# 10.2 Subject Accountability

Subject disposition will be summarized descriptively for all enrolled subjects. The summary will include the number of subjects who are enrolled and dosed with IP, who complete the study, who complete IP, and who withdraw prematurely including reasons

for withdrawal. In addition, the summary will include the date of study initiation (ie, first patient enrolled, last subject enrolled) and the date of study completion (ie, last subject last visit).

# 10.3 Important Protocol Deviations

Important Protocol Deviations (IPDs) categories are defined by the study team before the first subject's visit and updated during the IPD reviews throughout the study prior to database lock. These definitions of IPD categories, sub-category codes, and descriptions will be used during the course of the study. The final IPD list is used to produce the Summary of IPDs table and the List of Subjects with IPDs Demographic and Baseline Characteristics.

Subject demographic and baseline disease characteristics will be summarized descriptively for all enrolled subjects. Demographic data collection including sex, age, race, height, weight, body mass index and ethnicity will be collected in order to study their possible association with subject safety and treatment effectiveness. The baseline disease summary will include duration of disease, presence of psoriatic arthritis, reasons for apremilast failure, history of tobacco use, history of alcohol use, and the baseline value of each efficacy measure. A summary of prior psoriasis medication use, tabulated by preferred term, will be tabulated also.

# 10.4 Efficacy Analyses

The primary analysis for all efficacy endpoints will be conducted using the full analysis set.

For the primary analysis, all efficacy endpoints will be analyzed using LOCF method for missing data imputation. For all the efficacy endpoints, analyses on observed cases will be performed as sensitivity analyses. In addition, a sensitivity analysis for the primary endpoint will be performed using non-responder imputation as described in Section 9.3.2.

Summary statistics will be generated as well as 95% confidence intervals for the estimated responses. For absolute improvement and percent improvement endpoints, both 95% confidence intervals and p-values will be provided. No multiplicity adjustments will be made for the p-values.

	dpoint Summary Table	
Endpoint	Primary Summary and Analysis Method	Sensitivity Analysis
Primary Endpoint		
PASI 75 at week 12	
 
Full analysis set with LOCF imputation for missing data
 
	
 
Full analysis set using observed cases
 
Full analysis set with NRI imputation for missing data
 
Full analysis set with possible covariates
 

Secondary Endpoint		

 
PASI 75 at all other visits
 
PASI 50 and 90 at all visits
 
Percent PASI improvement from baseline at all visits
 
sPGA of 0 or 1 at all visits
 
sPGA of 0, 1, or 2 at all visits
 
sPGA at all visits
 
One and two grade improvement from baseline in sPGA at all visits
 
Percent BSA improvement at all visits
 
PSI total and component scores at all visits
 
Patient Assessment of Treatment Satisfaction at week 12 and 24
 
Exploratory Endpoints
 
	
 
Full analysis set with LOCF imputation for missing data
 
	
 
Full analysis set using observed cases
 


 
PASI 50, 75 and 90 at all visits
 
Percent PASI improvement at all visits
 
sPGA of 0 or 1 at all visits
 
sPGA of 0, 1, or 2 at all visits
 
sPGA at all visits
 
One and two grade improvement in sPGA at all visits
 
Percent BSA improvement at all visits
 
PSI total and component scores at all visits
 
Patient Assessment of Treatment Satisfaction at week 12 and 24
 
Improvement in DLQI at week 12 and 24
 
	
 
By reasons of apremilast failure (failure to achieve adequate response, loss of adequate response or intolerability)
 
Full analysis set with LOCF imputation for missing data
 
	Full analysis set using observed cases

# 10.4.1 Analyses of Primary Efficacy Endpoint

The primary analysis for the primary efficacy endpoint will estimate the proportion of subjects achieving PASI 75 at week 12. The primary analysis for the primary efficacy endpoint will be conducted using the full analysis set and LOCF imputation for missing post-baseline data. Sensitivity analyses will be performed using observed cases, non-responder imputation.

# 10.4.2 Analyses of Secondary Efficacy Endpoints

The primary analysis for the secondary efficacy endpoints will estimate the efficacy responses throughout the study. The primary analysis for the secondary efficacy endpoints will be conducted using the full analysis set and LOCF imputation for missing post-baseline data. Secondary efficacy endpoints will also be analyzed using observed cases.

# 10.4.3 Analyses of Patient Reported Outcomes Endpoints

The health related quality of life endpoints in this study include the DLQI, Patient Assessment of Treatment Satisfaction and PSI (See Appendix C). These endpoints are considered secondary and will be analyzed as described in Appendix C as well.

DLQI will be summarized as absolute score, absolute improvement, and percent improvement from baseline for total score and the following subscales: Symptoms and Feelings, Daily Activities, Leisure, Work and School, Personal Relationships, and Treatment. The proportion of DLQI responders, defined as subjects who achieve a 5 point or greater improvement from baseline or 0-score, will be summarized. In addition, the proportion of subjects who achieve a DLQI 0 or 1 score will be summarized.

Patient Assessment of Treatment Satisfaction will be summarized as categorical data.

PSI and component scores will be summarized as absolute score at all visits.

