1.2 Secondary

To evaluate the effect of treatment with etanercept on other efficacy endpoints (PASI, Static Physician's Global Assessment [sPGA], Body Surface Area [BSA]), and patient reported outcomes (PRO), including Psoriasis Symptom Inventory (PSI), Patient assessment of Treatment Satisfaction, and Dermatology Life Quality Index (DLQI).

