2.4 Rationale

Limited data is available on the efficacy and tolerability of etanercept in patients with inadequate response to apremilast. This study will evaluate the use of etanercept in subjects with inadequate response to apremilast for reasons of either primary failure, secondary failure or intolerability. There is a current trend of Dermatologists adopting the use of apremilast as an oral therapy option for psoriasis. Despite the convenient administrative route, it is anticipated that there may be a growing population of active psoriasis patients who will need to be switched or require additional therapy for reasons of failure to respond to apremilast or intolerance to apremilast. This study aims to characterize the response to etanercept in this population. There is also a need to better understand patient oriented measures in psoriasis patients, and this study seeks to characterize PRO including a novel instrument termed the PSI, in response to etanercept treatment.

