10.1.1.2 Secondary Endpoints

- PASI 75 at all other visits
- PASI 50 and 90 at all visits
- Percent PASI improvement at all visits
- sPGA of 0 or 1 at all visits
- sPGA of 0, 1, or 2 at all visits
- sPGA at all visits
- One and two grade improvement in sPGA at all visits
- Percent BSA improvement at all visits
- PSI total and component scores at all visits
- Patient Assessment of Treatment Satisfaction at week 12 and 24
- Improvement in DLQI at week 12 and 24

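### On the visible text, PSI is summarised only as absolute scores, so the secondary objective on PSI gets no paired estimate of change from baseline and no confidence interval for that change

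*SAP*

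**What the plan says.** - **Objective and rationale.** Protocol 1.2 opens its secondary objective with "To evaluate the effect of treatment with etanercept on other efficacy endpoints" and names PSI among the patient-reported outcomes covered. Protocol 2.4 says "this study seeks to characterize PRO including a novel instrument termed the PSI, in response to etanercept treatment".
- **Data.** PSI is completed at baseline, at home in weeks 1 to 3, and at every treatment visit (Protocol Table 1 and 7.3.12.1). SAP 10.3 summarises the baseline value of each efficacy measure.
- **Endpoint.** Protocol 10.1.1.2 lists "PSI total and component scores at all visits", a score rather than a change. SAP 4.1.2 and the SAP endpoint table use the same form.
- **PSI analysis.** SAP 10.4.3: "PSI and component scores will be summarized as absolute score at all visits".
- **DLQI analysis, same section.** "DLQI will be summarized as absolute score, absolute improvement, and percent improvement from baseline for total score", followed by subscales and a responder definition.
- **Interval rules, SAP 10.4.** In general: "Summary statistics will be generated as well as 95% confidence intervals for the estimated responses". For change: "For absolute improvement and percent improvement endpoints, both 95% confidence intervals and p-values will be provided".
- **Appendix C.** SAP 10.4.3 adds for the patient-reported outcomes: "These endpoints are considered secondary and will be analyzed as described in Appendix C as well". Only the title of Appendix C, which refers to forms and instruments, can be read in the available text.

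**The concern.** The objective asks about an effect of treatment, the trial has no control arm, and a baseline PSI is taken. Change within subject is the natural way to express such an effect, and the plan uses it for the other quantitative disease measures: percent improvement for PASI and BSA, one- and two-grade improvement for sPGA, and absolute and percent improvement for DLQI. PSI, the instrument that the rationale singles out as novel, is the exception, and no reason is given.

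Because PSI is not listed as an improvement endpoint, the rule in SAP 10.4 that gives intervals for change does not reach it. A reader of the planned tables could subtract the baseline mean from a later mean but could not attach a valid interval to the result. If PSI change were computed later to fill the gap, it would be an analysis added after the plan was set, and its selection could be questioned.

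**Working it through.** **The plan's own precision figure.** The only sizing figure concerns PASI 75, not PSI: a 95% confidence interval half-width below 15% at n = 80 and a 40% response (Protocol 10.2, SAP 3.2). Wald: 1.96 × √(0.4 × 0.6 / 80) = 10.7%, interval 29.3% to 50.7%. Clopper-Pearson for 32/80: 29.2% to 51.6%, average half-width 11.2%. The figure reproduces and the point on PSI does not touch it.

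**What the planned PSI tables would contain.** SAP 10.1 gives number of observations, mean, standard error, SD and quantiles. For PSI these would be available at baseline and at each visit, as levels.

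**What is needed for change.** With SDs s0 (baseline) and s1 (visit), correlation r and the same n subjects at both times:

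- Var(mean change) = (s0² + s1² − 2·r·s0·s1) / n

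The tables give s0, s1 and n, but not r, so the interval for change cannot be recovered from them.

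**Size of the gap.** Assume equal SDs. Then:

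- SE treating visits as independent = SD × √(2/n)
- SE paired = SD × √(2(1 − r)/n)
- ratio paired/independent = √(1 − r)

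Half-width of the 95% interval for change = t(0.975, 79) × SD × √(2(1 − r)/80), with t = 1.990. The documents give neither r nor the SD of PSI. Both ranges below are assumptions.

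| r | SE ratio | Paired SE smaller by | Half-width, SD units | Half-width in points, SD 5 to 9 |
|---|---|---|---|---|
| 0 (independent) | 1.00 | – | 0.31 | 1.6 to 2.8 |
| 0.3 | 0.84 | 16% | 0.26 | 1.3 to 2.4 |
| 0.5 | 0.71 | 29% | 0.22 | 1.1 to 2.0 |
| 0.7 | 0.55 | 45% | 0.17 | 0.9 to 1.6 |

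At r = 0.5, an interval built as if the visits were independent would be 1/√0.5 = 1.41 times too wide. With unequal SDs the ratio becomes √(1 − r·2·s0·s1/(s0² + s1²)). The added factor is at most 1, so equal SDs give the largest saving for a given positive r.

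**Scale.** Eight items scored 0 to 4 give a range of 0 to 32 if the total is their sum. The visible text does not define the total.

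**Who is in each mean.** SAP 9.3.1 and 9.3.2 neither impute a missing baseline nor carry baseline forward. Under LOCF, a subject with a baseline PSI and no later PSI counts at baseline only. In the observed-case analysis the set can differ at every visit. A paired summary removes this mismatch.

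**The case against.** The strongest reply is that the SAP does what the protocol defines. The PSI endpoint is worded as a score in both documents, while percent PASI, percent BSA and DLQI are worded as improvement in the same lists. That stands. A reader might infer that the SAP contradicts the protocol endpoint, but it does not: the gap lies between the objective and the analysis.

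Second, Appendix C is cited for analysis and cannot be read. Its title suggests mainly questionnaires, but the point has to be conditional on it.

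Third, a reader might infer that PSI has no confidence interval or no stated precision at all. The documents do not support this. The general rule in SAP 10.4 can be read as giving a 95% interval for the PSI level at each visit, and SAP 10.1 gives SDs and standard errors. Only the interval for change is absent.

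Fourth, it is tempting to say that change is the only measure of response in a single-arm trial. The plan itself uses absolute status as response, for example sPGA 0 or 1 and DLQI 0 or 1. The visible text defines no such threshold for PSI, but the general statement would be wrong.

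Fifth, a reader might infer a material bias from shifting denominators. The rule applies to all efficacy endpoints, and PSI is collected often, so few subjects are likely to lack every post-baseline value. Under LOCF the effect is probably small. It could be more visible in observed cases or in the intolerability group of 10 to 20 subjects.

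Last, adding PSI change brings it under the SAP 10.4 rule that attaches unadjusted p-values to improvement endpoints. For the total and 8 items at up to 9 post-baseline time points, that is 9 × 9 = 81 p-values before the observed-case repeats and the repeats by reason for apremilast failure. This stands, and the added wording must deal with it.

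**Conclusion.** The point holds as an inexpensive improvement, not as an error that threatens the trial. On the visible text, the secondary objective on PSI gets no paired estimate of change and no interval for change, and the planned summaries cannot supply that interval. The paired standard error would be about 16% to 45% smaller than one assuming independence. This rests on assumed correlations of 0.3 to 0.7 and equal SDs, and the comparison is with what a reader might compute, not with an analysis that the plan proposes. At n = 80, change could be estimated to within about 0.17 to 0.26 SD under the same assumptions.

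The primary endpoint, the sample size and the benchmark for the PASI 75 lower bound are untouched. If Appendix C already specifies PSI change with intervals, the point is met.

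**What to change.** First check Appendix C. Unless it already covers PSI change, add to SAP 10.4.3:

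> *Improvement from baseline (Section 6) in PSI total and component scores will be summarized with 95% CI at each post-baseline visit, in subjects with baseline and post-baseline values (LOCF, and observed cases as sensitivity). CIs are descriptive, and the p-value rule in Section 10.4 is not applied to the PSI item scores.*

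Keep the absolute scores. If Appendix C does not define the PSI total, define it in the same place.

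The baseline is already collected and SAP Section 6 already defines improvement for scores where lower is better, so no visit, assessment or subject is added. The cost is additional columns in tables that are already planned.

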# 10.4.4 Covariate and Subgroup Analyses

The following predictors and subgroup analyses may be performed to assess their influence on the primary endpoint:

- Body mass index ( $\leq 35 \text{ kg/m}^2 \text{ or } > 35 \text{ kg/m}^2$ )
- Body Weight (≤ median, > median)
- Age (<65, ≥ 65)
- Gender (male vs. female)
- Race (white, non-white)

- Ethnicity (Hispanic or Latino, Non-Hispanic or Latino)
- Baseline PASI score (≤ median, > median)
- Baseline BSA with psoriasis involvement (%) (≤ median, > median)
- History of psoriatic arthritis (yes, no)
- Baseline sPGA score (3, 4 or 5)

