10.1.3 Covariates and Subgroups

The following predictors and subgroup analyses may be performed to assess their influence on the primary endpoint:

- Body mass index (≤ 35 kg/m² or > 35 kg/m²)
- Body Weight (≤ median, > median)
- Age (<65, ≥ 65)
- Gender (male vs. female)
- Race (white, non-white)
- Ethnicity (Hispanic or Latino, Non-Hispanic or Latino)
- Baseline PASI score (≤ median, > median)
- Baseline BSA with psoriasis involvement (%) (≤ median, > median)
- History of psoriatic arthritis (yes, no)
- Baseline sPGA score (3, 4 or 5)

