10.2 Sample Size Considerations

This study will estimate the proportion of subjects with PsO who achieve a PASI 75 after 12 weeks of treatment with etanercept following failure of treatment with apremilast.

In recent etanercept studies, the 12-week PASI 75 response rate for etanercept was ~50 to 60%. The assumed response for a population with failure of treatment with apremilast is 40%. In placebo-controlled phase 3 studies, the PASI 75 placebo response rate was ~5% in subjects with moderate to severe plaque PsO. Therefore, in this single-arm study if the lower bound of the 95% confidence interval for the proportion of PASI 75 response is above 10%, we can safely conclude that in spite of limitations of a single-arm study (ie, regression to the mean and/or placebo effect), the etanercept effect is real.

The sample size of 80 is more than adequate to achieve a half-width of less than 15% for the 95% confidence interval for the proportion of subjects who achieve a PASI 75 response, assuming a sample proportion of 40% and a lower bound of the confidence interval above 10%.

In a phase 3, randomized, double-blind, placebo-controlled apremilast trial, 17% of subjects reported diarrhea and/or nausea. Of the 80 subjects enrolled, 60 subjects will be enrolled for reasons of primary or secondary failure to apremilast in the investigator's opinion. In addition, between 10 and 20 (up to 25%) will be enrolled for reasons of intolerability to apremilast in the investigator's opinion.

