# 3. Study Overview

# 3.1 Study Design

This is a multicenter, open-label, single-arm, phase 4 estimation study in subjects with PsO who have failed apremilast. Approximately 80 subjects will be enrolled in the study, among which at least 10 subjects (and not to exceed 20) will be enrolled for reasons of intolerability to apremilast in the investigator's opinion. The remaining 60 to 70 subjects will be enrolled for reasons of primary or secondary failure to apremilast in the investigator's opinion. The study consists of up to a 45 day screening period, a 24-week treatment period with study visits every 4 weeks, and a 30-day follow-up period for safety. Etanercept dosing will follow the recommended label dosing for patients with plaque PsO.

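### For the optional analyses of influence on Week 12 PASI 75, BMI, weight, age, baseline PASI and baseline BSA are specified only as two-way splits; a continuous term would use the 80 subjects considerably better

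*SAP*

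**What the plan says.** SAP 10.4.4 gives the purpose in one sentence: "The following predictors and subgroup analyses may be performed to assess their influence on the primary endpoint". In the list that follows, each continuous variable has two levels. Three are cut at the sample median: body weight, baseline PASI ("Baseline PASI score (≤ median, > median") and baseline BSA ("Baseline BSA with psoriasis involvement (%) (≤ median, > median"). Two have fixed cuts: age at 65 years and BMI at 35 kg/m². Protocol 10.1.3 has the same list with the same cuts, including "Body Weight (≤ median, > median".

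SAP Table 1, in Section 10.4, adds a sensitivity analysis of the primary endpoint described as "Full analysis set with possible covariates", without a model. SAP 10.1 also says that the primary endpoint may be examined with covariates, and it points to Section 4.2. That section uses the same cuts but omits body weight and ethnicity, which 10.4.4 includes. Section 4.2 in turn lists the reason for apremilast failure, which 10.4.4 leaves to 10.4.5.

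Neither document mentions a continuous term, a trend or a spline for any of these variables.

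**The concern.** A two-way split treats subjects just either side of the cut as different, and treats all subjects on the same side as alike. If response changes smoothly with weight or severity, much of the information about that relation is thrown away. With about 80 × 0.40 = 32 responders expected, there is little to spare.

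Two things are at stake if these analyses are run. A real predictor becomes more likely to be missed, and any estimated influence is less precise, which matters in an estimation study even without a formal test. In addition, a contrast at this sample's median weight, PASI or BSA cannot be reproduced directly in another study. That second complaint does not apply to the fixed cuts for age and BMI.

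**Working it through.** **Inputs from the documents.** Sample size: "Approximately 80 subjects will be enrolled in the study" (SAP 3.1). Assumed PASI 75 response: 40% (Protocol 10.2). Cut points: SAP 10.4.4 and Protocol 10.1.3. Entry limits that shape the distributions: weight below 264 lb and PASI of at least 10 (Protocol 4.1.1).

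**Inputs that are assumptions.** The documents give no distribution for any of the five variables and no effect sizes. Predictor shapes, odds ratios and the share of subjects beyond an off-centre cut are therefore assumed and varied.

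**Step 1: the plan's own precision figure.** Protocol 10.2 says: "The sample size of 80 is more than adequate to achieve a half-width of less than 15% for the 95% confidence interval". The Wald half-width is 1.96 × √(0.4 × 0.6 / 80) = 0.107, giving an interval of 29.3% to 50.7%. The Wilson half-width is 10.5 points and the Clopper-Pearson 11.2. The statement reproduces, and the covariate question does not touch it.

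**Step 2: information kept by a split.** For small linear effects, the share kept is the squared correlation between X and the indicator X > c. For a normal X with tail share p beyond c, this is φ(c)² / [p(1 − p)].

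| Cut (normal X) | Calculation | Kept | Lost | Equivalent n of 80 |
|---|---|---|---|---|
| Median | 0.399² / 0.25 | 0.637 | 36% | 51 |
| 15% tail | 0.233² / (0.15 × 0.85) | 0.426 | 57% | 34 |
| 11% tail | 0.188² / (0.11 × 0.89) | 0.361 | 64% | 29 |

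**Step 3: other shapes, median split.**

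| Assumed shape | Lost |
|---|---|
| Uniform | 25% |
| Normal weight capped at 264 lb (mean 190–230 lb, SD 40–60 lb) | about 33% |
| Normal PASI truncated at 10 | 34–38% |
| Lognormal, log-scale SD 0.3 to 1 | 41–73% |
| Exponential | 52% |

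These are small-effect values. In simulations with odds ratios from 0.67 to 0.40 per SD, the noncentrality ratio (split to continuous) was 0.67 to 0.70 for a normal predictor and 0.64 to 0.76 for an exponential one. The highest losses under skew therefore shrink when the effect is large.

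**Step 4: simulated power.** Logistic model, n = 80, marginal response 40%, normal predictor, score test at two-sided 5%, 40,000 trials. Type I error was about 5% for all three forms.

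| Odds ratio per SD | Continuous | Median split | 11% upper tail |
|---|---|---|---|
| 1.6 | 51% | 36% | 24% |
| 1.8 | 68% | 50% | 34% |
| 2.0 | 81% | 62% | 42% |

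The tail column is the least stable. A likelihood-ratio test gives 30% rather than 34% at an odds ratio of 1.8. Direction matters too: when the small group responds less often (odds ratio 0.57 per SD, 10% upper tail), power is 20%, against 64% for the continuous term.

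**The case against.** The strongest reply is that the plan commits to very little here. The analyses may or may not be done, no test or model is named, the objectives contain no predictor aim, and Protocol 10.3.1 makes p-values descriptive. The cuts stand under a joint heading for predictors and subgroups, so they could be read as defining the subgroup tables and leaving the covariate form open. This stands as a limit on importance. It does not remove the point: the two-group forms are the only ones written down, and an open model form is itself a reason to fix one before the data are seen.

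A split also need not lose information if the true effect is a threshold near the cut. That is correct, but neither document gives a threshold rationale for any cut, and a sample median is not chosen as one.

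Three stronger readings are tempting, and the documents do not support them.

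- A reader might take 36% as a floor for all five variables. It needs a normal predictor and a linear logit effect. The uniform case gives 25%, and weight under the entry cap about 33%.
- A reader might infer that the age cut must leave a very small group. No age distribution is given, so the 11% share is only an illustration.
- A reader might infer that identifying predictors is a main output of the study. Its stated purpose is to estimate one response proportion.

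Finally, the continuous form has costs of its own. Five terms entered jointly would leave 32 / 5, or about 6, responders per term, with weight and BMI, and PASI and BSA, plausibly overlapping. An odds ratio per sample SD would depend on the sample just as a median cut does. The fix has to avoid both.

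**Conclusion.** The point holds as a modest improvement to optional, exploratory analyses. The documents specify all five continuous variables only as two-way splits for judging influence on Week 12 PASI 75 (four of them in SAP 4.2, which omits weight). For a smooth effect the loss from a median split is material across the shapes tried: about 36% for a roughly normal predictor, about 25% for a uniform one and over 50% under strong skew, the last for small effects. An off-centre cut of a normal predictor loses more. At n = 80 and 40% response this means about 18 points of power at an odds ratio of 1.8 per SD (68% to 50%) for a median split, and about 34 points (68% to 34%) for an assumed 11% tail.

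The result rests on a monotone effect that is roughly linear on the logit, and on predictor distributions that the documents do not supply. The primary PASI 75 estimate and its confidence interval do not change.

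**What to change.** First align the list in SAP 4.2 with 10.4.4, since SAP 10.1 points to 4.2 and body weight is missing there. Then state in both sections that, if these analyses are performed, BMI, body weight, age, baseline PASI and baseline BSA each enter a logistic model for Week 12 PASI 75 as a continuous term, one predictor per model. Report each as an odds ratio with 95% CI per fixed unit, for example per 10 kg, 5 kg/m², 10 years, 5 PASI points and 10% BSA. Keep the listed categories for descriptive response-rate tables. SAP 9.6, which says that efficacy endpoints will not be analysed with parametric tests, needs a short clause so that it does not appear to rule this model out.

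The cost is some SAP wording and a few lines of model code on data already collected. The real downside is that linearity on the logit scale is assumed and can be checked only roughly with 80 subjects.
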